Primary objective: to establish the effects of critical illness and mechanical ventilation on thickness of the abdominal expiratory muscles.

Secondary objectives:

- to establish the effect of changes in abdominal expiratory muscle thickness on the expiratory muscle function.

	
 - to establish the correlation between changes in thickness of the abdominal expiratory and inspiratory muscles. - to study whether changes in the thickness of the abdominal expiratory muscles also affects weaning outcome, and ICU readmission due to respiratory complications.
Study design	Prospective cohort study.
Study population	Patients who have been mechanically ventilated at the intensive care unit (ICU)
Inclusive criteria	
 - Age > 18 years - Invasive mechanical ventilation < 48 hours - Expected duration of mechanical ventilation > 72 hours
Exclusive criteria	
 - Past medical history of neuromuscular disorders - Mechanical ventilation > 48 hours within the current hospital admission - BMI > 35 kg/m² - Pregnant women - Open abdominal wounds at proposed location of the ultrasound probe, due to recent abdominal surgery
Sample size	100 subjects
Recruiting subjects	
Because mechanical ventilation is a requirement for eligibility, the participants frequently will be incapable of consent at the time of inclusion. Therefore, we will ask delayed informed consent from the patient as soon as he/she is capable of providing consent.
 
If patients are not able to give consent during their hospital stay, we will send an opt-out letter to the patient.

Intervention	Data from ultrasound measurements and from the electronic patient record will be obtained / analyzed. One additional blood sample will be obtained within 24 hours after inclusion, during planned blood collection (from arterial line or venous puncture).
Study endpoint	- Thickness of the abdominal expiratory muscles (external oblique, internal oblique, transverse abdominis muscle), during the inspiratory and expiratory phases of breathing.

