Statistical Analysis Plan	
SPSS statistical software package version 22.0 or R software for statistical computing version 3.2.0 will be used.
 
Primary endpoint: change of thickness of expiratory abdominal muscles during MV. Change in thickness will be presented as ratio change compared to baseline, to account for inter-subject variation in baseline thickness. The Wilcoxon signed-rank test will be used to compare changes in baseline and nadir values.
 
Association of categorical independent variables (such as sex, use of corticosteroids during ICU stay, sepsis on admission, etc.) with nadir change in expiratory muscle thickness will be assessed using a Mann-Whitney U test. Association of continuous independent variables (such as duration of mechanical ventilation, days taken to wean, inflammation at inclusion, etc.) with nadir change in expiratory muscle thickness will be assessed using a linear regression model, with change in expiratory muscle thickness as dependent variable. Correlation between change in thickness during the acute stage of MV (5 days) with the total time spent on the ventilator will be examined using a linear regression model.
 
Correlation between diaphragm and expiratory muscles
 
Correlation between change in expiratory muscle thickness and change in diaphragm thickness will be assessed with Pearson's correlation test to compare population means. The difference between change in

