	
expiratory muscle thickness and change in diaphragm thickness will be assessed with a Student's t-test that is paired per subject. This will be done by using the change in thickness between baseline and the last data point obtained. Second, this will be evaluated by using the slope of the thickness curves assessed with a goodness of fit model. We will use a goodness of fit model to first describe the course of both diaphragm and expiratory muscle thickness for each subject. The type of model will be determined after data is obtained.
 
Subgroup analysis
 
Based on the outcomes of these analyses, a subgroup analysis may be performed to compare the subjects with high change in expiratory muscle thickness, to a group with low change in expiratory muscle thickness. A cutoff value to divide these groups will be determined based on how data will emerge. Variables as respiratory function measurements can be compared between groups with a Student's t-test, using group average values. Further, a Kaplan-Meier survival analysis will be carried out to quantify differences in time to wean between groups.

Referenties
	

- and endotracheal tube pressure with bilateral anterolateral magnetic phrenic nerve stimulation in patients in the intensive care unit. *Crit Care Med* 2001; 29:1325-31.

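### The primary test compares baseline with nadir; if the nadir is each patient's lowest of two or more later scans the test is invalid, and if most patients have such scans it usually declares thinning when nothing has changed

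*Combined protocol and SAP*

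**What the plan says.** The primary objective is neutral about direction: "to establish the effects of critical illness and mechanical ventilation on thickness of the abdominal expiratory muscles". The design is a single cohort of 100 subjects with no comparison group.

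Under Primary endpoint, the Statistical Analysis Plan expresses change as a ratio to baseline and names one test: "The Wilcoxon signed-rank test will be used to compare changes in baseline and nadir values". It does not say what the nadir is, whether baseline itself may count as the nadir, how many scans each patient has or when, or what significance level applies.

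Nadir change then becomes a per-patient outcome. Categorical factors are compared on it by Mann-Whitney test, and continuous ones by linear regression: "Association of continuous independent variables (such as duration of mechanical ventilation, days taken to wean, inflammation at inclusion, etc.) with nadir change".

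Under Correlation between diaphragm and expiratory muscles, the plan intends to "describe the course of both diaphragm and expiratory muscle thickness for each subject" and to take slopes from those curves, although "The type of model will be determined after data is obtained". The same section uses a different quantity, the "change in thickness between baseline and the last data point obtained". Several scans per patient are therefore implied, and the nadir is not simply the last scan.

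**The concern.** The signed-rank test assumes that, when nothing changes, within-patient differences are centred symmetrically on zero. A minimum picked from several later scans breaks this. Each scan carries error, and choosing the lowest one chooses negative error, while the baseline is a single unselected scan. The difference is pushed below zero before any biology enters, and with no control group nothing absorbs the artefact.

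The only test named for the primary endpoint could then report thinning whether or not it occurred, and could hide or reverse a modest thickening, which the objective leaves open. The secondary analyses inherit the problem. Patients ventilated longer probably have more scans and so a lower minimum, which can produce an apparent link between thinning and duration of ventilation.

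**Working it through.** **Inputs from the documents.** 100 subjects; within-patient comparison; ratio scale; signed-rank test. The sample size has no effect size, SD, level or power behind it, so there is no figure of the plan's own to reproduce.

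**Inputs assumed because the documents give none.** Two-sided 0.05; k later scans per patient; scan-to-scan CV of 5% unless stated (the Rationale claims reliability but gives no error figure); constant true thickness.

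**Step 1: probability that the nadir lies below baseline.** With exchangeable errors, baseline is equally likely to take any rank among the k+1 scans. The nadir exceeds baseline only if baseline is the lowest, which has probability 1/(k+1). So P(nadir < baseline) = k/(k+1): 1/2, 2/3, 3/4 and 5/6 for k = 1, 2, 3 and 5.

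**Step 2: a check that needs no simulation.** Replace the signed-rank test by a sign test that calls thinning when at least 61 of 100 patients fall below baseline. Under p = 1/2 the chance is P(Bin(100, 1/2) ≥ 61) = 1.8%. Under p = 2/3 it is 90.3%, and under p = 3/4 it is 99.9%.

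**Step 3: the planned test, simulated on the ratio scale** (5,000 trials per row).

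| Later scans k | P(nadir < baseline) | Sign test, thinning | Signed-rank, significant | Median spurious loss |
|---|---|---|---|---|
| 1 | 1/2 | 1.8% | 5.4% (both directions) | 0 |
| 2 | 2/3 | 90.3% | 98.1% (all thinning) | 2.8% |
| 3 | 3/4 | 99.9% | 100% (all thinning) | 4.2% |
| 5 | 5/6 | 100% | 100% (all thinning) | 5.8% |

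The last column follows from the median shift in units of the single-scan SD, which is 0.556, 0.835 and 1.151 for k = 2, 3 and 5. Multiplied by 5% these give 2.8%, 4.2% and 5.8%. At 2% CV the shifts for k = 3 and 5 are 0.835 × 2% = 1.7% and 1.151 × 2% = 2.3%. Precision therefore shrinks the false loss but hardly changes the false-positive rate.

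**Step 4: correlated errors.** On the difference scale with k = 2, autoregressive errors (correlation 0.5-0.95) give 90.7-95.7% and a driftless random walk gives 89.6%; at k = 3 all are 99.8% or more. With correlation 0.8 and 5% CV the median false loss falls to 1.9% (3 scans) and 3.0% (5 scans).

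**Step 5: only some patients have two later scans, the rest one.** The average probability of falling below baseline is f × 2/3 + (1 − f) × 1/2, where f is the fraction with two scans. For f = 25%, 50% and 75% this is 0.542, 0.583 and 0.625. Simulated false-positive rates are about 15%, 45% and 81-87%.

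**Step 6: associations with no true change.** With an assumed median of 7 ventilation days (log SD 0.6) and scans every 1-3 days, regression of nadir change on ventilation time was significant in 65-92% of trials across all runs. Equal scan counts do not make the group comparisons safe. With 50 v 50 patients and CVs of 4% v 6%, the Mann-Whitney test rejected in 25% (3 scans) and 46% (5 scans). With one scan, rejection stayed nominal at 4-6%.

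**The case against.** The strongest reply is that the nadir is undefined, so the defect is conditional. That stands. With one later scan per patient the test is valid. If the nadir were a single time point chosen for its lowest group mean, simulated rejection is 3-10% over 2-7 scans, near nominal at the low end and modestly inflated at the high end. That reading fits poorly with a plan that regresses each patient's nadir change on covariates, but the text does not exclude it.

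A second reply is that the nadir is a legitimate measure of maximum loss. It is, as a description. The fault lies in testing it against one unselected baseline scan.

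A reader might infer that the trial is bound to report false thinning. The documents do not support that: they give no scan counts, and if only a quarter of patients had two later scans the false-positive rate would be about 15%. Nor does the argument show that real thinning is absent; it shows that this test cannot tell. A reader might also suppose that the separately planned five-day change is a nadir. The plan does not say how that change is taken, so this is a point to clarify and not a finding.

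**Conclusion.** The point holds in conditional form and should be fixed before analysis. If the nadir is each patient's lowest of two or more later scans, which is the ordinary meaning of the word and fits the per-patient curves, the primary test is invalid whatever the ultrasound precision. If most patients have such scans, it will usually declare thinning when nothing has changed: about 98% with two scans and 100% with three or more, against about 5% with one. The false loss is about 3-6% at 5% CV with two to five independent scans, and less with more precise or correlated scans.

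These rates assume 100 evaluable patients, a two-sided 0.05 level and constant true thickness. With fewer evaluable patients the two-scan rate falls (difference scale: 84.1% at 50, 43.0% at 20).

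Associations with nadir change are biased whenever scan count, ventilation duration or measurement error varies with the covariate. It would be wrong to conclude that Mann-Whitney comparisons are safe when groups have equal numbers of scans.

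**What to change.** Make the primary analysis a change not selected for being lowest, using one of these:

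- **(a)** A Wilcoxon signed-rank test on the log ratio of the scan nearest a prespecified day (for example day 5, the plan's own acute stage) to the baseline scan, if such scans exist. The log ratio also removes the slight excess seen on the raw ratio scale with one scan (5.4% at 5% CV, 7.3% at 15%).
- **(b)** A mixed model of log thickness on all scans, with random intercept and slope and flexible time. Report the ratio to baseline at a prespecified day with a 95% CI. Count time from the baseline scan, because patients may enter up to 48 hours into ventilation.

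For either option, define the nadir, say whether baseline can count, and report it descriptively with the scan count and no p-value. State how the five-day change is taken. Use the non-nadir change in all association analyses.

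In simulations with no true change, a linear-time mixed model rejected in 3.5-7.5% and a five-day Wilcoxon test in 5.5-7.5% (200 trials per setting), while the nadir test on the same data declared thinning in 98-100%. Those runs assumed dropout unrelated to thickness and did not include flexible time. Linear time lost power for an immediate 5% rise (77% against 100% for the five-day test), which is why (b) asks for flexible time.

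Option (b) costs only SAP wording if the implied repeat scans exist; (a) also needs scans near the chosen day, which must be checked. The apparent loss will be smaller under both. Option (a) loses patients who leave the ventilator before that day, or uses an earlier scan for them. Option (b) assumes that dropout through extubation or death is ignorable given the observed scans, so a sensitivity analysis should be added.

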Expiratory muscle function in critically ill ventilated patients

NTC:

Date of approved by METC: February 14, 2017

Date of amendment approved by METC: May 22, 2019

Rationale	
Inspiratory muscle weakness develops rapidly in ventilated critically ill patients¹⁻⁴ and is associated with adverse outcome, including prolonged duration of mechanical ventilation and mortality.⁵⁻⁷ Surprisingly, the effects of critical illness on expiratory muscle function have not been studied.
 
The main expiratory muscles are the abdominal wall muscles, including the external oblique (EO), internal oblique (IO) and transversus abdominis muscles (TRA).^{8,9} These muscles are activated when respiratory drive or load increases, which can be during e.g. exercise,¹⁰⁻¹² diaphragm fatigue,¹³ increased airway resistance, or positive airway pressure ventilation.¹⁴ The abdominal wall muscles are also critical for protective reflexes, such as coughing.¹⁵ Reduced abdominal muscles strength may lead to decreased cough function^{16,17} and thus inadequate airway clearance.¹⁸ This will lead to secretion pooling in the lower airways, atelectasis, and ventilator associated pneumonia (VAP).^{19,20} Studies have shown that decreased cough function is a risk for weaning failure and (re)hospitalization for respiratory complications.²¹ Further, high mortality was found in patients with low peak expiratory flow.²²
 
Considering the importance of a proper expiratory muscle function in critically ill patients, it is surprising that the prevalence, causes, and functional impact of changes in expiratory abdominal muscles thickness during mechanical ventilation (MV) for critically ill patients are still unknown.

------------------	--

Ultrasound is increasingly used in the ICU for the visualization of respiratory muscles. In a recent pilot study we confirmed the feasibility and reliability of using of ultrasound to evaluate both diaphragm and expiratory abdominal muscle thickness in ventilated critically ill patients (manuscript in preparation). An example of such measurement can be found in figure 1. Accordingly, the primary aim of the present study is to evaluate the evolution of abdominal expiratory muscle thickness during MV in adult critically ill patients, using ultrasound data.

Figure 1. Left: ultrasound of the abdominal expiratory muscles (EO, IO, TRA). Right: anatomical overview of the abdominal muscles. RA = rectus abdominis, less involved in respiration

Objective

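### The primary test and the nadir-based associations are insensitive to muscle thickening and lean towards thinning, although the objective and endpoint have no direction

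*Combined protocol and SAP*

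**What the plan says.** The objective is direction-neutral: "to establish the effects of critical illness and mechanical ventilation on thickness of the abdominal expiratory muscles". So is the primary endpoint in the Statistical Analysis Plan, "change of thickness of expiratory abdominal muscles during MV". The scale of measurement can carry a sign: "Change in thickness will be presented as ratio change compared to baseline, to account for inter-subject variation in baseline thickness".

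The test is different: "The Wilcoxon signed-rank test will be used to compare changes in baseline and nadir values". The association analyses follow it. Categorical variables are related to the nadir ("with nadir change in expiratory muscle thickness will be assessed using a Mann-Whitney U test"), and the regressions on continuous variables take nadir change as well. The plan does not define the nadir, and in particular does not say whether the baseline scan can itself be the lowest value.

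Under Subgroup analysis the plan allows, as an option, a comparison of two groups: "compare the subjects with high change in expiratory muscle thickness, to a group with low change in expiratory muscle thickness". The cutoff is left until the data are seen, and no direction is given.

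Three measures do carry a sign. One is the 5-day change: "Correlation between change in thickness during the acute stage of MV (5 days) with the total time spent on the ventilator" is to be examined by linear regression. The other two are the change from baseline to the last data point and the fitted slope for each subject, both described under the comparison with the diaphragm.

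**The concern.** The Rationale treats the direction of change as open. It says that nothing is known about "the prevalence, causes, and functional impact of changes in expiratory abdominal muscles thickness", and that these muscles are activated by higher drive or load and by positive airway pressure. Nothing there rules out that some patients' muscles thicken.

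The lowest of several scans answers a narrower question: how thin did the muscle ever become? Patients who thicken are pulled towards zero, while patients who thin keep their full change. Reading error adds a second push in the same direction, because the minimum of several noisy readings is set against a single baseline reading. At stake is the headline result. A cohort that is stable, or that moves in both directions, could be reported as thinning. The associations with sex, corticosteroids, sepsis and the other listed variables would then rest on the same distorted score. The high/low split would not help, because it has no separate group for thickening.

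**Working it through.** **Inputs from the documents.** Baseline-against-nadir Wilcoxon test; ratio to baseline; 100 subjects. The documents give no derivation of the 100, so there is no planned figure to reproduce. They also give no scan schedule and no measurement error.

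**Assumptions, not in the documents.** K = 3, 5 or 7 follow-up scans; reading-error SD (CV) 3, 5 or 8% of baseline; true change linear in time, reaching ±20% at the last scan; two-sided 5% test; 300 simulated trials per setting.

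**Step 1, no reading error.** A steady riser is at 20/K % at the first follow-up scan, which is the lowest later value.
- K = 3: 20/3 = +6.7%. K = 5: 20/5 = +4.0%. K = 7: 20/7 = +2.9%.
- If baseline is eligible, the nadir is baseline and the score is 0% for every K.
- A steady faller scores −20% in every case.

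**Step 2, nobody changes.** For three scans the expected minimum of normal errors is −3/(2√π) = −0.846 SD. At CV 5% this is −0.846 × 5% = −4.2%, the same as the simulated median. Thinning was declared in 100% of simulated trials in every setting. The signed baseline-to-last change rejected in about 3 to 8%, with a median of about 0.

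**Step 3, simulated medians.** Each cell gives CV 3 / 5 / 8%.

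| Scans | Nobody changes, baseline not eligible | All rise 20%, baseline not eligible | All rise 20%, baseline eligible |
|---|---|---|---|
| 3 | −2.5 / −4.2 / −6.7% | +6.6 / +6.0 / +4.6% | 0 / 0 / 0% |
| 5 | −3.5 / −5.7 / −9.2% | +3.7 / +2.5 / +0.2% | 0 / 0 / −0.4% |
| 7 | −4.0 / −6.7 / −10.7% | +2.2 / +0.7 / −2.1% | 0 / −0.1 / −2.1% |

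The signed last-scan change has a median of about +20% throughout when all rise. If baseline is eligible, no patient can score above zero, so every non-zero difference is negative and the test can reject only towards thinning.

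**Step 4, mixed cohorts.**
- 25% thin, 50% stable, 25% thicken: thinning was declared in 94 to 100% of trials. With baseline not eligible, 6 to 60% of true thickeners scored zero or below; with baseline eligible, all did. Patients above +10% made up 0.7 to 10.7% of the cohort by nadir (baseline not eligible) and 25 to 30% by last scan.
- 20% thin, 60% stable, 20% thicken, five scans: the nadir test declared thinning in 100% of trials. A signed last-scan test rejected in about 5%, because the two directions cancel. A signed test alone therefore does not describe such a cohort; the share in each direction is needed too.

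**Step 5, the two-group split.** On a signed scale with a cutoff for loss, thickeners join the stable patients. On an absolute scale they join those who thin. A cutoff for increase is not excluded by the text, but two groups cannot separate thinning, stable and thickening.

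**The case against.** The strongest reply is that the plan is not blind to increases. The 5-day change, the baseline-to-last change and the per-subject slopes are all signed. A reader might infer that thickening is invisible, or that the trial can only report thinning or no change; the documents do not support that. Nor does the nadir always hide a uniform rise. If baseline is not eligible and every patient thickens by 20%, the planned test declares thickening in 99 to 100% of trials with three scans and in 100/98/7% with five (CV 3/5/8%). With seven scans the figures are 100/22/0%. Complete erasure requires baseline to count as the nadir, which the plan leaves open.

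This limits the claim but does not remove it. The 5-day change enters only a regression with ventilator time. The other two measures are described only for the diaphragm comparison, and the curve model is to be chosen after the data are obtained. None of them is the primary result, and none reports how many patients increase.

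Three further cautions stand. The high/low split is optional and its direction is unspecified. Prevalence appears in the Rationale and is not promised in the Objective. A reader might also infer that a link between ventilator time and both extremes of change would be missed, but no section says that both extremes prolong ventilation, and any power figure for that shape depends on an invented symmetric effect.

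**Conclusion.** The concern holds for the primary test, the nadir-based associations and the two-group split; it does not extend to the whole plan. Nadir scoring reduces a true rise of 20% to a median between −2.1% and +6.6% if baseline is not eligible, and to zero or below if it is. It also declares thinning in a cohort where nothing happens.

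The sizes depend on the assumed number of scans, reading error and linear course. The direction does not: a minimum cannot exceed any of the values it is taken from, and more scans or more error lower it further. The signed secondary measures show that the information will be collected, but they do not repair the primary result. This should be corrected before the data are analysed.

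**What to change.** Changes to the Statistical Analysis Plan:
- **Primary measure.** Signed ratio change from baseline, estimated by a mixed model over all scans, with the estimate and 95% CI at day 5, the time point that the plan already uses for the acute stage. Inclusion requires only an expected ventilation time above 72 hours, so some patients may have no day-5 scan. The model uses their earlier scans, on the assumption that missing scans are explained by the observed data. Numbers extubated early or dead by day 5 should be reported beside the estimate.
- **Associations.** Use the same signed change in place of nadir change.
- **Direction.** Report the percentages that decrease, stay stable and increase beyond a prespecified threshold tied to measurement error, with 95% CIs. State which patient value is classified. Use these three groups in place of high/low.
- **Nadir.** Define it, including whether baseline is eligible, and keep it as description only.
- A squared term is at most an exploratory addition to the model of 5-day change and ventilator time. It does not fit the regressions in which thickness change is the dependent variable.

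The cost is SAP text and a little more analysis, with no measurements beyond the serial scans that the plan already relies on. There are two downsides. Three groups are smaller than two: an observed 20/100 has an exact 95% CI of 12.7 to 29.2%. The threshold also needs a repeatability figure, which the documents do not give, although the Rationale mentions a reliability pilot. With single readings it would be 1.96 × √2 × CV, which is 8.3, 13.9 or 22.2% at CV 3, 5 or 8%. At the highest error, a 20% change would therefore count as stable.

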Study parameters	
 - Thickness of the diaphragm muscle - Inflammatory markers (TNF-alpha, IL-6, IL-10) at inclusion (measured from blood sample using ELISA technique). - Respiratory function parameters: maximum inspiratory pressure (MIP), maximum expiratory pressure (MEP), cough peak flow (CPF), diaphragm pressure and diaphragm electrical activity (in selected patients with these measurements available in clinical practice). - Mechanical ventilation parameters. - Weaning outcome - Ventilator associated pneumonia (VAP) - Follow-up of 6 weeks: readmission to ICU / hospital, reason for readmission, pneumonia acquired after discharge when subject is hospitalized. - Critical illness parameters (e.g. medication, APACHE II score) - Patient characteristics (e.g. gender, age, neurological and cardiopulmonary co-morbidities, BMI) 
This data will be retrieved from the electronic patient record and anonymously filed in a database.
 
Data on muscle thickness (thickness of diaphragm muscle and expiratory muscles) will be collected directly

	from ultrasound measurements on the ultrasound device.

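### No covariate adjustment is prespecified for any between-patient association, so illness severity can produce an apparent link between thickness change and weaning or expiratory function

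*Combined protocol and SAP*

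**What the plan says.** The Study design row describes a "Prospective cohort study", with no randomised exposure and no comparison group. Under Objective, two secondary objectives are worded causally: "to establish the effect of changes in abdominal expiratory muscle thickness on the expiratory muscle function", and whether thickness changes "also affects weaning outcome, and ICU readmission due to respiratory complications".

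The Statistical Analysis Plan covers between-patient questions as follows.

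- Categorical factors (sex, corticosteroid use, sepsis): "sepsis on admission, etc.) with nadir change in expiratory muscle thickness will be assessed using a Mann-Whitney U test".
- Continuous factors, and early (5-day) change against total ventilator time: linear regression, with no covariates named.
- Respiratory function in high- versus low-change groups (Subgroup analysis): Student's t-test.
- Time to wean in the same groups: "a Kaplan-Meier survival analysis will be carried out to quantify differences in time to wean between groups".

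Study parameters lists "Critical illness parameters (e.g. medication, APACHE II score", together with age, gender, BMI and neurological and cardiopulmonary co-morbidities. No analysis gives any of these a role as an adjustment variable. The only allowance for differences between patients is that thickness is expressed as a ratio to the patient's own baseline. That deals with baseline thickness, not with severity.

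**The concern.** Sicker patients may plausibly be more often septic, receive corticosteroids more often, lose more muscle, perform worse on pressure and cough tests, and wean later. If so, thickness change will be associated with weaning time and with function even when it has no direct bearing on either. An unadjusted comparison cannot tell these situations apart.

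At stake are the two secondary objectives on function and on weaning. The subgroup t-test is the only named analysis of expiratory function, and the Kaplan-Meier comparison is the only named time-to-event analysis of weaning. A difference found by either could be read as the effect that the objective asks about. Readmission, which is part of the weaning objective, has no named analysis at all.

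**Working it through.** **Inputs.** The documents give n = 100 and the list of tests. They give no alpha, effect size, power or correlation, so there is no stated figure to reproduce. Assumed: two-sided alpha 0.05; a severity variable S that correlates r with each of the two variables compared; no direct link between those two; complete data.

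**Step 1. Which tests can adjust?**

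| Question | Planned method | Adjustment |
|---|---|---|
| Baseline to nadir (primary) | Wilcoxon signed-rank | Within patient; not needed for severity |
| Expiratory muscle versus diaphragm change | Paired t-test; Pearson correlation | The first is within patient; the second is worded as a correlation |
| Categorical factors | Mann-Whitney | Not possible |
| Continuous factors; early change and ventilator time | Linear regression | Possible, none named |
| Respiratory function | Student's t-test | Not possible |
| Time to wean | Kaplan-Meier by group | Not possible for a continuous score |

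**Step 2. Linear regression without severity.** The induced correlation is ρ = r × r. With Fisher's transformation, z = atanh(ρ) × √(100 − 3), and the rejection rate is Φ(z − 1.96) + Φ(−z − 1.96).

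- r = 0.2: ρ = 0.04, z = 0.39, rate 7%.
- r = 0.3: ρ = 0.09, z = 0.89, rate 14%.
- r = 0.4: ρ = 0.16, z = 1.59, rate 36%.
- r = 0.5: ρ = 0.25, z = 2.52, rate 71%.

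Simulation agrees: 7%, 15–16%, 35% and 71–73%.

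**Step 3. Mann-Whitney.** The binary factor is a latent normal score, correlated r with S, cut so that 30–40% of patients are exposed. Simulated rates are about 6% at r = 0.2, 9–12% at 0.3, 21% at 0.4 and 47–50% at 0.5. The spread reflects the share exposed and simulation error. With r = 0 the rate is 4%.

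**Step 4. With severity in the model.** The linear models return to 4–5% for every r from 0.2 to 0.5, if S is measured without error. If the score captures a share q of the variance of S, the remaining partial correlation is (r² − q r²) / (1 − q r²), tested with √96 in place of √97.

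- r = 0.5, q = 0.5: (0.25 − 0.125) / 0.875 = 0.143, rate 29%.
- r = 0.5, q = 0.7: (0.25 − 0.175) / 0.825 = 0.091, rate about 15%.
- r = 0.3, q = 0.5 to 0.7: rate about 6–7%.

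These values of q are assumptions. Adjustment removes much of the problem, not all of it.

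**Step 5. Which change to use for weaning.** The plan's factor analyses use nadir change. A patient ventilated longer has more scans and so more chances of a low value, which ties nadir to time on the ventilator by construction. This was simulated with no true effect, n = 100, wean time 3 days plus an exponential with mean 7 days, 10% measurement noise, and scans daily or every third day (all assumed). A severity-adjusted Cox model on nadir change rejected in 75–93% of runs. Change fixed at day 5, in patients still ventilated then and with time counted from day 5, rejected in about 5%. Adjusting for severity without fixing the time of measurement would therefore not repair the weaning analysis.

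**The case against.** Several points on the other side stand.

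- A reader might infer that every planned association is unadjusted. For linear regression the text does not say so: covariates are unspecified, not excluded. Choosing them after the data are seen is still a prespecification gap.
- A reader might extend the point to the primary objective, "to establish the effects of critical illness and mechanical ventilation on thickness of the abdominal expiratory muscles". The documents do not support that. The named test compares each patient with himself or herself, and critical illness is part of the stated exposure, so adjusting for APACHE II would remove some of what is being studied. The lack of a control group is a separate matter that covariates cannot mend.
- A reader might say that sepsis and corticosteroids will be reported as causes of muscle loss. The plan calls those analyses associations, and those factors are not among the secondary objectives. Mann-Whitney is a valid test of the marginal association. Its rejections count as false positives only if the question is whether the link remains at equal severity.
- A reader might attach a log-rank error rate to the weaning comparison. The plan names no log-rank test and no median split; the cutoff is left to the data, and the subgroup analysis is optional. No such rate is claimed here.
- The correlations are assumed, and at 0.2 there is almost no inflation.

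What remains is that the function and weaning objectives are causally worded and served by methods that cannot account for severity. The plan does not label these analyses exploratory.

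**Conclusion.** The concern holds in this form: no covariate adjustment is prespecified for any between-patient association, and the tests named for categorical factors, respiratory function and time to wean cannot adjust for a severity score that the study collects. Severity can therefore create an apparent link between thickness change and weaning or function.

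For the conditional association with n = 100, the false-positive rate is about 6–7% when both correlations are 0.2, roughly 9–16% at 0.3 and 47–73% at 0.5, against about 5% with severity in the model and measured without error. These figures are for Mann-Whitney and linear regression, and they rest on assumed correlations, so they show what can happen rather than what will. The primary within-patient test is untouched. This is a change that should be made; it does not invalidate the study.

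**What to change.** 1. **Weaning.** Add a Cox model, cause-specific with death as a competing event, of time to wean counted from day 5. The predictor is continuous thickness change from baseline to day 5, the acute stage the plan already uses. Include only patients still ventilated at day 5, and adjust for APACHE II, age and cardiopulmonary co-morbidity. Do not use nadir change as the predictor.
2. **Respiratory function.** Replace the high/low t-test with linear regression on continuous thickness change, adjusted for APACHE II, age, sex and BMI.
3. **Factors associated with thickness change.** Put each factor (sepsis, corticosteroids, each of the three inflammatory markers) in its own linear model of the log thickness ratio, adjusted for the same four covariates, with 95% confidence intervals. That is five coefficients, or 100 / 5 = 20 patients per coefficient with complete data. Keep the unadjusted tests as descriptive. Separate models are preferable because corticosteroid use during the ICU stay is post-baseline and may lie downstream of sepsis.
4. **Wording.** Phrase the function and weaning objectives as *association with*.

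The cost is analysis-plan text and modest analysis time, since the covariates are already collected. A few degrees of freedom are spent. Patients weaned before day 5 leave the weaning model; under the wean-time assumption in the working, exp(−2/7) = 0.75, so about 75 of 100 would remain. Function data may exist for fewer than 100 patients, which would lower the ratio for item 2. Residual confounding remains, because APACHE II captures severity only in part.
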